**Protocol of BIC study**

This document presents the protocol of Brief Motivational Intervention and Long-term Regular Follow-up Contact Program (BIC), a pre-post study that aims to provide a global treatment action to combat suicide.

The study is based on the WHO protocol of the SUPRE-MISS study, part of the WHO worldwide initiative for prevention of suicidal behaviors (1) and the Veterans Affairs Brief Intervention and Contact Program (VA BIC), a brief educational intervention and regular contacts for patients from a VA mental health unit (2). The current study will use sociodemographic, clinical, and psychosocial questionnaires in suicide attempters presenting at Emergency Departments.

# I. BIC Study Protocol

## Background

The Suicide PREvention Multisite Intervention Study on Suicidal Behaviors (SUPRE-MISS) was piloted by the WHO center in Geneva, along with the collaboration of the National Centre for Suicide Research and Prevention of Mental Ill-Health (NASP) at Karolinska Institutet, in the early 2000s. The SUPRE-MISS study was conducted in five countries (Brazil, India, Sri Lanka, the Islamic Republic of Iran and China) and evaluated in an RCT. In this RCT, suicide attempters who came to the emergency department were identified and allocated to either Treatment as usual (TAU) or TAU and Brief Intervention Contact (BIC). A total of 1867 suicide attempters were randomized to TAU (n=845) or to TAU and BIC (n=922). The BIC was an hour-long individual information session about reasons for suicide attempts and possibilities for help and treatment. After this information session, delivered by a person with clinical experience, suicide attempters were followed-up for 18 months with nine follow-up contacts in between. The primary outcome measure was suicide at 18-months follow-up.

The current study, BIC study, is a replication of the SUPRE-MISS pilot study where the results have been published in 2008. The current BIC study was initially developed to fit the context of the COVID-19 pandemic, but it is now being deployed in different centres despite being out of the COVID-19 pandemic circle.

Why the need for the BIC study?

- The Supre-MISS study has shown significant results
- Despite the COVID-19 being more prominent between 2020 and 2022, suicide rates initially decrease but then increase during crisis such as national epidemics.
- The impact of the COVID-19 pandemic will continue to overshadow the lives of many and precipitate in negative life events such as increased alcohol consumption, smoking, worse mental health, worse somatic health, unexpected life changes and higher suicide rates.

The objectives of the BIC study are:

- To raise awareness about mental health, suicide and suicidal behaviors among health care professionals
- To inform good treatment routine among emergency doctors and psychiatry staff
- To raise awareness about mental health, suicide and suicidal behaviors among the general population
- To evaluate the effectiveness of a Brief Motivational Intervention and Long-term Regular Follow-up Contact Program in reducing death by suicide
- To assess the mechanism by which the BIC intervention works
- To draw similarities of suicide prevention and treatment effectiveness across different countries
- To pinpoint differences of suicide prevention and treatment effectiveness among different countries

## Aim

The overall aim of the BIC study is to evaluate a treatment and prevention practice that aims at reducing morbidity and mortality associated with attempted and completed suicide, and to raise awareness about suicide, suicidal behaviours and mental health in different cultural and social backgrounds.

## Methodology

The methodology is based on the SUPRE-MISS and Veterans study. The effectiveness of SUPRE MISS was evaluated and shown effective in an RCT where the treatment group received TAU reinforced with a brief intervention contact (BIC) with 9 follow-ups after discharge in comparison to control group receiving only TAU and a follow-up at 18 months after suicide attempt.

The BIC study is currently being carried out or is in the process of being carried out in four countries, namely Brazil, Sweden, India, and the USA. More countries are encouraged to carry out the BIC study.

## II. BIC RCT Study

### Trial design

The study will be a multicenter randomized (1:1) control trial (RCT). Enrolment including eligibility screening and randomization into either the intervention or control group will be conducted according to the WHO randomization methods. Suicide attempters assigned to the COVID-19 BIC group will receive in-person motivational and awareness increasing interview using the COVID-19 BIC method (Annex 1) described separately. These interviews will be conducted by trained health care professionals (eg: a doctor, a nurse, a psychiatrist, a psychologist) one day before or on the day of discharge. The training for the health care professionals will be given on a social media platform where a group training will take place.

Baseline assessments will be conducted after randomization and last follow-up will be 18-month post intervention with intermediate follow-ups by online trained volunteers (eg: volunteers from NGOs, individuals working with mental health, community workers, medical students, research assistants) at the 1, 2, 4, 8, and 12 weeks and then at 4, 6, 12, and 18 months.

A back-up supervisory system will be established to support the health care professionals as well as for the volunteers if they encounter any problems during the interview or during the follow-ups.

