## Assessment and Evaluation

A comprehensive assessment will be conducted before the intervention to establish a baseline for each participant. Follow-up assessments will be conducted following follow-up time.

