## Evaluation Procedures

### Evaluation procedures

Data will be collected at baseline and at 18 months follow-up for all participants. The details of the suicide attempt according to the ICD-10 codes and Medical Damage Scale (MDS) will also be evaluated at baseline along with a series of mental and physical health status.

The following scales are mandatory and will be administered at each site:

- *COVID-BIC Questionnaire (questions about Social, Economic and Health aspect)*- adopted from [https://www.iasp.info/pdf/ICSPRC\\_COVID\\_advice\\_on\\_questions.pdf](https://www.iasp.info/pdf/ICSPRC_COVID_advice_on_questions.pdf)
- *Medical Damage Rating Scale (MDRS)* which assesses the degree of medical lethality of a suicide attempt (5)
- *The Patient Health Questionnaire (PHQ-9)* which measures depressive symptoms (7)
- *Athens Insomnia Scale (AIS)* which assesses any sleep difficulty (8)
- *Generalized Anxiety Disorder (GAD-7) Scale* which measures worry and anxiety symptoms (9)
- *Multidimensional Scale of Perceived Social Support (MSPSS)* which measures perceived social support from friends, family and significant other (10)
- *Interpersonal Needs Questionnaire-15 (INQ-15)* which measures thwarted belongingness (TB) and perceived burdensomeness (PB) (11)
- *Paykel Suicide Scale (PSS)* which measures suicidal ideation and attempts (12)
- *Suicide Related Coping Scale (SRCS)* which measures measure knowledge and confidence in using internal coping strategies and external resources to manage suicidal thoughts and urges (13)
- *WHO Well-Being Scale (WHO-5)* which evaluates mood, vitality, and general interests (14)

Additional questionnaires can be added if there are additional data that a site would like to collect. However, these additional questionnaires similar to the above scales should be translated into the local language of each site, adapted to consider the cultural specificities and pilot-tested to assess the validity (if it has not been used in similar settings before).

The following socio-demographic data will be collected at baseline: age, sex, country of birth, marital status, living arrangement, residence area, employment status, education level, income level, religion affiliation and sexual orientation.

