There will be follow-up contacts at nine timepoints for those in the intervention group and one follow-up at 18-month for those in the control group. These follow-ups will be conducted using a questionnaire template (Annex 3) and will follow-up if the participant is still live, any consequent suicide attempt, and the well-being of the participant.

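### Baseline is taken after randomisation, and the protocol does not withhold the allocation until it is complete, so self-reported baselines may differ by arm and bias any analysis that uses them

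*Protocol*

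**What the plan says.** Four parts of the protocol bear on the timing of baseline.

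- **Trial design** (section II) describes a 1:1 randomised trial and says "Baseline assessments will be conducted after randomization". It places eligibility screening within enrolment, together with randomisation. Those allocated to BIC "will receive in-person motivational and awareness increasing interview".
- **Assessment and Evaluation** says "A comprehensive assessment will be conducted before the intervention to establish a baseline for each participant".
- **Evaluation procedures** says "Data will be collected at baseline and at 18 months follow-up for all participants". It lists the mandatory scales, including PHQ-9, GAD-7, AIS, WHO-5, MSPSS, INQ-15, PSS and SRCS, and says that the "Medical Damage Scale (MDS) will also be evaluated at baseline". It adds: "There will be follow-up contacts at nine timepoints for those in the intervention group and one follow-up at 18-month for those in the control group".
- **Participants** makes an MDS score of 2 or above part of how a suicide attempter is identified and plans a separate analysis stratified by MDS. **Exclusion criteria** ties one exclusion (condition not permitting an interview) to the MDS score.

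No section describes masking of participants or assessors, or says when either learns the allocation.

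**The concern.** A baseline is useful because treatment assignment cannot have influenced it. Taking it before randomisation guarantees this. Taking it after randomisation leaves it dependent on nobody who answers or scores the questions knowing the arm.

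Here that protection is thin. One arm receives a face-to-face session and repeated contacts, and the other receives usual care and one contact at 18 months, so the difference cannot be hidden from participants. The eight scales listed above rest on the participant's own answers. A person just told that they will, or will not, receive extra support may answer questions on mood, support, belongingness or coping differently. An assessor who knows the arm may also ask them differently.

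Two further weaknesses follow from the same ordering. People lost between allocation and baseline are randomised without a baseline, and that loss can differ by arm. And for controls, who have no BIC session, the requirement that baseline precede the intervention sets no clear time limit.

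At stake are analyses that use baseline values: change scores, baseline-adjusted comparisons, and work on the protocol's stated objective of assessing how the intervention acts. Later analysis cannot fully repair this, because a baseline collected in the wrong order cannot be collected again.

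**Working it through.** **1. Does another section move baseline ahead of randomisation?** No. Trial design puts it after randomisation, and Assessment and Evaluation puts it before the intervention. Both hold if the order is randomisation, baseline, intervention. The second statement narrows the window but leaves baseline after allocation.

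**2. Which stated outcomes use a baseline value?** The primary outcome is suicide death at 18 months and uses none. The secondary outcomes (other deaths, well-being, depressive symptoms, sleep and anxiety, social connectedness) are all defined at 18 months. The protocol names no change-from-baseline or baseline-adjusted model.

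**3. The plan's own figure.** Inputs from the Sample size section: 3% versus 1%, two-sided 5% (the protocol writes this as 95%), 80% power.

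- Without continuity correction: n = [1.960·√(2·0.02·0.98) + 0.842·√(0.03·0.97 + 0.01·0.99)]² / 0.02² = (0.3881 + 0.1662)² / 0.0004 = 768.0, or 769 per arm rounded up.
- With continuity correction: n′ = (n/4)·[1 + √(1 + 4/(n·0.02))]² = 865.1, or 866 rounded up.

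The stated 865 per group (1730 in total) is reproduced. No baseline value enters, so the order of baseline and randomisation does not change it.

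**4. Size of the possible bias.** The protocol gives neither a shift nor a correlation, so both are assumptions. Let s be the arm-related shift in reported baseline, in SD units, and r the baseline-to-18-month correlation. Take m = 865 per arm, full follow-up, no true effect and equal SDs.

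- 18-month values alone: bias 0, SE = √(2/m) = 0.0481.
- Change score: bias of size s, SE = √(2 − 2r)·√(2/m).
- ANCOVA: bias of size r·s, SE = √(1 − r²)·√(2/m).
- With z = bias/SE, the rejection rate of a two-sided 5% test is 1 − Φ(1.96 − z) + Φ(−1.96 − z).

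For s = 0.1:

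| r | Change score: bias, SE, z | Rejects | ANCOVA: bias, SE, z | Rejects | 18-month values alone |
|---|---|---|---|---|---|
| 0.3 | 0.10, 0.0569, 1.76 | 42% | 0.03, 0.0459, 0.65 | 10% | 5% |
| 0.5 | 0.10, 0.0481, 2.08 | 55% | 0.05, 0.0416, 1.20 | 22% | 5% |
| 0.7 | 0.10, 0.0372, 2.68 | 77% | 0.07, 0.0343, 2.04 | 53% | 5% |

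At r = 0.5, a shift of 0.05 SD gives 18% (change score) and 9% (ANCOVA); a shift of 0.2 SD gives 99% and 67%. With s = 0, as when baseline precedes allocation, both methods return to zero bias and 5%.

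**5. MDS, sections side by side.** Participants and Exclusion criteria use MDS to decide who enters, so the score is needed at screening. Evaluation procedures has MDS evaluated at baseline, and Trial design puts baseline after randomisation. Taken literally, these statements give MDS two different times. The protocol does not say whether it is scored once or twice, or which score defines the strata.

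**The case against.** The strongest reply is that nothing the protocol defines as an outcome depends on baseline. Primary and secondary outcomes are all set at 18 months, and the comparison closest to that wording, 18-month values alone, is unbiased by this route whatever the shift. Change-score or ANCOVA use would be set in a SAP not shown here. This stands, and it limits the point to analyses that use baseline. It does not remove the point: the protocol collects a baseline for every participant and sets mechanism as an objective, and the order of collection is fixed in the protocol itself.

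Second, being randomised is not the same as being told. The protocol does not say when participant or assessor learns the arm, and it refers to WHO randomisation methods without describing them. Nine contacts against one make the arm obvious later, but do not show that it was known at baseline. This also stands. The bias is conditional, and its direction and size cannot be obtained from the document. Nor does the protocol give any figure for baseline data missing differently by arm.

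Third, a reader might infer that eligibility itself is decided after allocation, so that exclusions could depend on arm and reach the primary outcome. The document does not support this. Eligibility screening is placed within enrolment alongside randomisation, and the case definition and exclusion need MDS at that stage. Evaluating MDS at baseline does not show that it is first scored then. MDS also rates the medical damage of an attempt already made, so it is less exposed to knowledge of the arm than self-reported mood. What remains is an ambiguity to reconcile.

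**Conclusion.** The point holds in limited form and should be fixed. The protocol fixes a weak order, baseline after randomisation, with nothing to keep the arm unknown until baseline is complete. If the arm is known by then, change-score, baseline-adjusted and mechanism analyses of the self-reported scales can be biased. With an assumed shift of 0.1 SD, false-positive rates would be about 42% to 77% for change scores and 10% to 53% for ANCOVA over correlations of 0.3 to 0.7. These figures are illustrations, resting on an assumed shift, full 18-month follow-up of 865 per arm, and analyses that the protocol does not name.

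It would be wrong to conclude that the trial's main result is compromised. Suicide death at 18 months, the sample size and unadjusted 18-month comparisons are untouched by the self-report route. That participants cannot be masked is inferred from the nature of the intervention and the lack of any masking statement.

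The assessment takes the randomised design of section II as given. The introduction's description of a pre-post study, and the BIC Intervention section's statement that all participants receive BIC, conflict with that design and need separate reconciliation.

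**What to change.** Replace the sentence on baseline timing in Trial design with:

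> Consent, eligibility (including MDS scoring) and the baseline battery are completed before randomisation, or at minimum before the allocation is disclosed to participant and assessor.

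Then align the other sections. Assessment and Evaluation should refer to randomisation (or disclosure of the allocation) as well as to the intervention, so that the same limit applies to controls. Evaluation procedures should state that the MDS score used for eligibility and for the strata is the one recorded before allocation.

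The change needs no new instrument and no larger sample. Its cost is that some baseline interviews are spent on people who are then not randomised, and the protocol gives no basis for saying how many. Since the mandatory list has ten instruments and the setting is an emergency department, this burden may not be trivial. Where a site cannot complete the battery before randomising, the minimum option, with the allocation undisclosed until the baseline form is closed, gives the same protection against an arm-related shift in the answers.

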### Participants

All suicide attempters who visit the emergency department and meet the inclusion criteria during a 12-month period will be asked to participate in the study.

*Suicide attempt* is defined as a nonfatal self-directed potentially injurious behavior with any intent to die as a result of the behavior. A suicide attempt may or may not result in injury. Suicide attempters will be diagnosed according to the ICD-10 as well as a score of 2 or above on the Medical Damage Scale (MDS) (5).

The number of participants for each of the site can be determined based on the catchment area, but the emergency department of the study unit should serve at least a population of 250,000. This

estimate was adopted from the MONSUE study, A European Multicentre Study on Suicidal Behaviour (6).

Each site in the respective country is requested to translate instruments used in this study into the local language. All suicide attempters will be included in the analysis, but a separate analysis will be conducted by stratifying suicide attempters according to their different MDS score.

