### Primary Outcome

Hypothesis: The BIC will significantly lead to a reduced death by suicide at 18-months follow-up than treatment as usual.

Outcome measure: death from suicide at 18-month follow-up

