## Sample size

The sample size will be estimated based on the SUPRE-MISS study that evaluated the effectiveness of BIC in suicide attempters that visited the emergency department. Centres recruit a minimum of 1730 subjects (865 per treatment group) considering a significance level of 95% (two-sided), power of 80% and assuming 3% suicides in the TAU and 1% in the BIC group at 18-months follow-up.

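### Analysing MDS strata separately, and looking for country differences, is likely to suggest differences in effect that do not exist if done on suicide death with about 35 expected events; use one interaction model and descriptive stratum estimates

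*Protocol*

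**What the plan says.** The Participants section keeps everyone in the main analysis and adds that "a separate analysis will be conducted by stratifying suicide attempters according to their different MDS score". It gives an entry threshold for the MDS (2 or above), but no number of strata, cut-points, outcome or test.

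The objectives in the Background include "To pinpoint differences of suicide prevention and treatment effectiveness among different countries". The Methodology section names four countries, "namely Brazil, Sweden, India, and the USA", and invites more. No outcome or method is attached to this objective.

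The only stated hypothesis and the only powered comparison are overall. Primary Outcome gives "Outcome measure: death from suicide at 18-month follow-up". Sample size works from "assuming 3% suicides in the TAU and 1% in the BIC group at 18-months follow-up", and states that "Centres recruit a minimum of 1730 subjects (865 per treatment group").

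**The concern.** A separate analysis in each stratum answers whether BIC beats TAU in that stratum. It does not answer whether the effect differs between strata. When strata are small, a mix of significant and non-significant results is common even if the true effect is the same everywhere. Such a mix is easily read as BIC working at some damage scores, or in some countries, and not in others.

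That matters here because the primary outcome is rare and the trial is sized only for the pooled comparison. A false claim that the programme fails in one country or severity group could affect whether it is offered there.

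**Working it through.** **Inputs (protocol).** 3% suicides on TAU and 1% on BIC at 18 months; 865 per arm; 1:1 allocation; two-sided test; power 80% (Sample size, Trial design). The stated 95% significance level is read as alpha = 0.05.

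**Assumptions (not in the protocol).** The stratified and country analyses use suicide death; 1730 is the trial total; strata are equal in size; the 3% and 1% rates hold in every stratum; there are no losses.

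**Reproducing the plan's figure.** Without continuity correction:

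n = [1.96·√(2·0.02·0.98) + 0.8416·√(0.03·0.97 + 0.01·0.99)]² / 0.02² = 768.0, or 769 per arm.

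With continuity correction:

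n = (768.0/4)·[1 + √(1 + 4/(768.0·0.02))]² = 865.1, or 866 when rounded up.

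The stated 865 is therefore the continuity-corrected figure. At 865 per arm, overall power is 84% (normal approximation) or 82% (Fisher).

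**Expected deaths.** 865·0.03 = 25.95 on TAU and 865·0.01 = 8.65 on BIC, 34.6 in all.

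**Splitting into k equal strata.** Let p be the exact Fisher power in one stratum. With independent strata, the chance that some but not all reach p<0.05 is 1 − p^k − (1 − p)^k.

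| k | Deaths per stratum, TAU v BIC | Fisher power p | Some but not all significant | All significant | None significant |
|---|---|---|---|---|---|
| 2 | 13.0 v 4.3 | 48.1% | 50% | 23% | 27% |
| 3 | 8.7 v 2.9 | 29.0% | 62% | 2.4% | 36% |
| 4 | 6.5 v 2.2 | 19.2% | 57% | 0.1% | 43% |
| 5 | 5.2 v 1.7 | 13.1% | 50% | <0.01% | 50% |

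Example for k = 3: 1 − 0.290³ − 0.710³ = 1 − 0.024 − 0.358 = 0.618.

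**Precision with four strata.** SE(log RR) = √(1/6.49 − 1/216 + 1/2.16 − 1/216) = 0.78. An observed risk ratio of 1/3 would carry a 95% interval of about 0.07 to 1.54. The chance that a given stratum shows at least as many deaths on BIC as on TAU is 0.088. The chance of this in at least one of four is 1 − (1 − 0.088)⁴ = 31%.

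**What an interaction test can detect on suicide death.** For two strata of 432.5 per arm, the variance of one log odds ratio is 1/12.98 + 1/419.5 + 1/4.33 + 1/428.2 = 0.313. The SE of the difference is √(2·0.313) = 0.79. The ratio of odds ratios needed for 80% power is exp(2.80·0.79), about 9. Power is 14%, 28% and 42% for ratios of 2, 3 and 4. For one pair among four countries the SE is 1.12 and the ratio needed is about 23.

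**Continuous outcomes for comparison.** With unit SD, no dropout and no baseline adjustment, the detectable treatment-by-stratum contrast is 2.80·√(4/n), with n per arm and stratum. This is 0.27 SD for two strata (n = 432.5) and 0.38 SD for one pair of four countries (n = 216.25).

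**The case against.** The strongest objection is that the protocol never says these analyses test suicide death. It sets no stratum p-values and no rule for comparing strata. The wording could describe a single stratified analysis beside the pooled one. The country aim is one of several broad objectives, and subgroup methods are usually left to a statistical analysis plan, which was not available here. This stands in part. A missing method is no fault, and a reader who infers that the plan commits to a suicide test in each stratum, or that its results are bound to mislead, goes further than the text. The protocol does, however, commit to a separate stratified analysis and to a country comparison, and its only hypothesis and sample size concern suicide death. That outcome is a natural reading, though not the only one.

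A second objection concerns the cell sizes. A reader might infer that every cell will hold only 2 to 7 deaths. That is the result for four equal strata with 1730 as the trial total, and the protocol fixes neither. If 1730 is per centre, each centre expects about 35 deaths, four single-centre countries expect about 138 (4·34.6), and the small country cells do not arise. The trial-total reading fits better: site numbers are to follow the catchment area, the size is based on a five-country trial, and 1730 from the minimum catchment of 250,000 in the 12-month recruitment period would be 0.69% of that population. The text still does not settle it.

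A third objection is that an interaction model does not rescue the mortality question. This stands in full, as the detectable ratios above show. The model is the correct form for a claim of difference, but it adds no information. Moving the country question to well-being or depression scores would change the question, because those are measured only in survivors who respond.

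**Conclusion.** The concern holds in limited form. If the MDS and country analyses are applied to suicide death and 1730 is the trial total, within-stratum power is below 50% for any split into two to five equal strata. A mixed pattern of significance would then arise in roughly half to three-fifths of trials with no true difference. Reading strata one by one is therefore likely, though not certain, to suggest differences that do not exist.

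The sizes depend on equal strata, constant 3% and 1% rates and the trial-total reading. On the per-centre reading the argument from small country cells falls away. The point that separate tests do not test a difference does not depend on the sample size: with four countries each at 82% power, a mixed pattern would still occur with probability 1 − 0.821⁴ − 0.179⁴ = 54%.

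The primary analysis is not affected.

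**What to change.** - Replace the separate MDS analysis with one model in all participants containing treatment, MDS score and their interaction.
- Report MDS-stratum and country-specific suicide results as descriptive estimates with 95% intervals, without stratum p-values.
- Base any statement that effectiveness differs by MDS or country on the interaction estimate and its interval.
- State that this interaction has little power for suicide death, so that its absence is not evidence of equal effect.
- State whether 1730 is the trial total or a number per centre.
- Optionally, add treatment-by-country interactions on the existing 18-month continuous outcomes. Label them supportive, note that they cover only responding survivors, and do not let them replace the suicide question.

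The cost is a change of wording and one model; no new data are needed. The price is that the trial can make no standalone claim about suicide death in a single MDS stratum or country.
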